6.1.7. Safety Evaluation Methods

6.1.7.1. Description of Safety Endpoints

1) Safety Endpoints

- Safety endpoints: Incidence of symptomatic intracranial hemorrhage within 24 h postoperatively, mortality within 90d, incidence of SAE, incidence of AE, and incidence of device defects.
- #### **2) Selection of Method and Time to Evaluate, Record and Analyze the Safety Endpoints**
- **Incidence of symptomatic intracranial hemorrhage within 24h**

Recording time and method: Symptomatic intracranial hemorrhage within 24h, specifically refers to intracranial hemorrhage (parenchymal hematoma, subarachnoid hemorrhage, ventricular hemorrhage) accompanied by neurological deterioration (NIHSS score increases by ≥ 4 compared with that preoperatively).

Incidence of symptomatic intracranial hemorrhage within 24 h = Number of subjects who develop symptomatic intracranial hemorrhage on CT or MR within 24 h in this group/Number of subjects who receive revascularization device for thrombectomy in this group $\times 100\%$.

* Subjects with symptomatic intracranial hemorrhage postoperatively who show additional hemorrhage on CT or MR within 24 h postoperatively will not be re-evaluated.

● All-cause mortality within 90 days

Recording time and method: Throughout the clinical trial. All-cause mortality = Number of deaths in this group/Number of subjects who receive revascularization device for proximal thrombectomy in this group $\times 100\%$.

● Incidence of device defects

Recording time and method: During the thrombectomy. Incidence of device defects = Number of defective devices / Total number of devices $\times 100\%$.

Note: The investigational device defects that occur during the clinical trial, such as device fracture and mislabeling.

● Incidence of SAE

Recording time and method: Throughout the clinical trial. Incidence of SAE = Number of subjects with SAE/Number of subjects treated with intracranial thrombectomy device for thrombectomy in total $\times 100\%$.

● Incidence of AE

Recording time and method: Throughout the clinical trial, incidence of AE = Number of subjects with AE/Number of subjects who receive intracranial thrombectomy device for thrombectomy $\times 100\%$.

6.2. Study Process

6.2.1. Study Process

6.2.1.1. Enrollment

The investigator will screen the subjects according to the inclusion and exclusion criteria after obtaining the ICF signed by the subjects (or their guardians). After the subjects pass the screening, at the end of cerebral DSA angiography and before using the revascularization device, the investigator will randomize the subjects into the test group and the control group in the randomization order, and the enrollment will be considered successful.

6.2.1.2. Randomization

Randomization will be performed via an electronic randomization system after screening for inclusion and exclusion criteria. The investigator will log into the randomization system, fill in the subject information and then submit, and the system will automatically give the randomization results. The investigator should select the corresponding test product to treat the subject according to the results given by the electronic randomization system. In Group A, Sinomed Neurovita Ghunter Revascularization Device will be used, and in Group B, Covidien Solitaire FR will be used. Once the subject information is entered into the electronic randomization system, no deletion will be allowed, and all operations will be automatically left on the system for verification.

6.2.1.3. Visit Schedule

1) Visit 1: Screening/baseline period (-1 d ~ 0 d)

After all the subjects (or their guardians) sign the ICF, the investigator will screen the subjects according to the inclusion/exclusion criteria of the study. During this period, the following visit contents need to be completed:

- i. Signing of ICF;
- ii. Recording of basic information of the subject;
- iii. Present medical history: onset time and admission time;
- iv. Medical history: history of allergy, history of stroke, history of other significant diseases (e.g., presumed septic emboli or suspected bacterial endocarditis), history of neurological diseases;
- v. Vital signs (blood pressure, heart rate);
- vi. NIHSS score;
- vii. MRS score, ASPECTS score (required within 6 - 24 h of onset);

Laboratory examination:

- viii. Pregnancy testing (Only for women of childbearing potential who are planning to become pregnant)
- ix. Administration of anticoagulant and antiplatelet drugs;
- x. Cerebral CT or MR will be performed, and the following information will be recorded:
 - a) When the onset time is ≤ 6 h, cerebral CT or MR is performed;
 - b) Cerebral CT or MR is performed when the onset time is 6 (exclusive)-24h (inclusive) to determine whether ASPECTS score ≥ 6 is met; (if immediate CT perfusion imaging or MR perfusion imaging is feasible, CTP or MRP is recommended to assist in the assessment of the infarct

core to determine whether ASPECTS score ≥ 6 is met).

* For laboratory tests and imaging tests, the results after this admission and the results of external hospital examinations within 24h preoperatively are acceptable.

c) Other significant abnormal conditions.

2) Visit 2 (0 d):

i. Recording of cerebral vascular DSA:

- a) Name of target vessel and lesion segment, proximal diameter of occluded vessel
- b) mTICI image grading postoperatively
- c) Does the patient suffer from carotid origin occlusion or carotid dissection or arteritis?
- d) Is the vessel access so tortuous that makes it difficult for the investigational/control device to reach the target location?

ii. Recording of the operations:

- a) Date of operation, femoral artery puncture time, operation start and recanalization time (or end time)
- b) Intraoperative treatment method (Are implant stent, balloon dilatation and antithrombotic drugs used)
- c) Model of each revascularization device, the frequency of thrombectomy procedure, evaluation of success rate of device operation, whether the vessel is successfully revascularized, recanalization success time, and reason for failure

iii. Administration of anticoagulant and antiplatelet drugs;

iv. Recording of adverse events;

v. Recording of device defects:

Note: The frequency of thrombectomy procedure with the thrombectomy device will be determined by the investigator on a case-by-case basis. If recanalization fails, the investigator may use other diagnostic and therapeutic measures (including but not limited to dual-stent technique, stent implantation, and aspiration device) according to specific case characteristics.

3) Visit 3: Observation period (V3: 24 ± 12 h postoperatively)

The subjects undergo clinical follow-up $24 \text{ h} \pm 12 \text{ h}$ postoperatively. All the visit information will be analyzed and recorded by investigators. In this visit, the following visit contents need to be completed:

- i. Vital signs;
- ii. NIHSS score;
- iii. Laboratory tests;
- iv. Cerebral CT or MR will be performed, and the following information will be recorded:
 - a) Is there intracranial hemorrhage (parenchymal hematoma, subarachnoid hemorrhage, ventricular hemorrhage)
 - b) Is there is a new cerebral infarction
 - c) Other significant abnormal conditions
- v. Administration of anticoagulant and antiplatelet drugs;
- vi. Recording of adverse events;
- 4) Visit 4: Follow-up period (V4: 7 ± 2 d postoperatively (before discharge in case of premature discharge))

The subjects undergo clinical follow-up 7 ± 2 d postoperatively. All the visit information will be analyzed and recorded by investigators. In this follow-up visit, the following visit contents need to be completed:

- i. Vital signs;
- ii. NIHSS score;
- iii. Laboratory tests (if laboratory test results had already been collected at Visit 3, they might not be collected here);
- iv. Administration of anticoagulant and antiplatelet drugs;
- v. Recording of adverse events;
- 5) Visit 5: Follow-up period (V5: 90 ± 14 d postoperatively)

[figure not shown]
The subjects undergo outpatient/telephone follow-up 90 ± 14 d postoperatively. All the visit information will be analyzed and recorded by investigators. In this follow-up visit, the following visit contents need to be completed:

- i. mRS score;
- ii. Administration of anticoagulant and antiplatelet drugs;
- iii. Recording of adverse events;
- 6) Premature termination of visit

Subjects can withdraw from the study at any time, and once a subject withdraws prematurely from the study before the end of the follow-up period, an premature termination visit must be completed as soon as possible and the reason for termination will be recorded. Evaluations to be performed during this follow-up

period is the same as Visit 5. All information will be analyzed and documented by the investigator.

Study Flowchart

Data Collection:

Visit time Visit contents	Screening/Baseline period	Treatment period	Observation period	Follow-up period	
	Preoperatively -1 d ~ 0 d	Day of operation/0 d	Postoperatively 24 h \pm 12 h	Postoperatively 7 d \pm 2 d	Postoperatively 90 d \pm 14 d
Signing of ICF	×				
Medical history	×				
Preoperative diagnosis	×				
Vital signs ¹	×		×	×	
NIHSS score ²	×		×	×	
mRS score ³	×				×
Laboratory test ⁴	×		×		
Pregnancy test ⁵	×				
Cerebral CT or MR ^{6,7}	×		×		
Cerebrovascular DSA ⁷	×				
Verification of eligibility criteria		×			
Randomization		×			
Operations		×			
Antiplatelet and anticoagulant medication	×	×	×	×	×
Adverse event		×	×	×	×
Device defect		×			

Note:

- 1) Vital signs include heart rate and blood pressure.
- 2) NIHSS score: assessing the degree of neurological impairment of the subject.
- 3) MRS score: assessing the degree of disability of the subject.
- 4) Laboratory tests (The laboratory test results at 24 h preoperatively are accepted during the screening period, and one laboratory test within 9d postoperatively is sufficient):

Blood routine: Red blood cell, hemoglobin, white blood cell count, and platelet count

Blood chemistry: Urea nitrogen (urea), serum creatinine, blood glucose

Coagulation: Prothrombin time, activated partial thromboplastin time and

INR

- 5) Only for women of childbearing potential who are planning to become pregnant, blood or urine pregnancy test result is acceptable.
- 6) Cerebral CT or MR is performed when the onset time is ≤ 6 h; cerebral CT or MR is performed when the onset time is 6 (exclusive)-24h (inclusive) to determine whether ASPECTS score ≥ 6 is met; (if immediate CT perfusion imaging or MR perfusion imaging is feasible, CTP or MRP is recommended to assist in the assessment of the infarct core to determine whether ASPECTS score ≥ 6 is met).
- 7) CT or MRI images and DSA images during thrombectomy are burned on a CD in DICOM format and evaluated by a central interpretation room.
- 8) Randomization: An electronic randomization system is logged into for randomization.

* If any of the micro-guidewire and microcatheter does not pass through the thrombus segment of the target vessel during the operation, or if the thrombectomy device is not used for thrombectomy, this subject is statistically processed as having a blank randomization number;

6.2.2. Device Specifications (recommend the operation method, and the operator may make slight modification according to the actual situations)

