6.1.5.3. Criteria and Procedures for Withdrawal from/Discontinuation of Trial Treatment

The subjects may withdraw from the study at any time during the course of the study without giving a reason: moreover, subjects may choose not to undergo any study procedures after signing the ICF, and if subjects choose not to undergo any study procedures after signing the ICF, the investigator must be informed. However, subjects have the right to continue receiving the standard of care regardless of the cases.

Any subject may also be withdrawn from the study by the investigator based on medical judgement.

Subject's premature discontinuation or withdrawal from the study can be any of the following cases, but not limited to:

- 1) The subject is unwilling to continue participating in this study for any reason;
- 2) For medical or safety reasons, the investigator believes that the subject should be withdrawn from the study;
- 3) Serious protocol violation (confirmed by the principal investigator);
- 4) The investigator or the sponsor requests to terminate the study for any reason;
or
- 5) Death.

For all subjects who terminate the study early, the investigator should make every effort to find out the reasons for withdrawal from the trial, for example: adverse

events, failure of corrective treatment, the investigator's decision or other reasons. The reasons for withdrawal should be recorded in the EDC. Subjects who withdraw early should be requested to complete an early withdrawal visit according to the visit schedule.

Subjects who withdraw from the study will not be replaced, i.e. the randomization number will be uniquely related to each subject and cannot be reused.

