Evaluation method: The recanalization time will be judged by intraoperative procedure and the vascular condition shown by imaging.

Formula: Recanalization time = Recanalization success time - Femoral artery puncture time

Precautions: The recanalization time is the time from the completion of femoral

artery puncture to recanalization success. If the vessel is not revascularized, the end time point is recorded as the time point at the end of operation. Criterion for instant recanalization success: target vessel recanalization with mTICI grade of 2b or 3 after thrombectomy with the investigational device. The investigator's judgment intraoperatively shall prevail.

- **Proportion of subjects with NIHSS score decrease > 4**

Recording time and method: The preoperative and postoperative NIHSS scores are compared by three time points: pre-operation, 24 ± 12 h postoperatively and 7 ± 2 d postoperatively (before discharge in case of premature discharge) to analyze the degree of impairment and improvement of neurological functions preoperatively and postoperatively. The NIHSS score is the total score based on NIHSS scale (as shown in Appendix 5).

Proportion of subjects with NIHSS score decrease > 4 = Number of subjects with NIHSS score decrease > 4 postoperatively in this group/Number of subjects treated with thrombectomy through stents in this group $\times 100\%$.

- **Success rate of device operation**

Definition: The success rate of device operation is the proportion of device operation success. Device operation success is defined as successful delivery of the investigational device to the diseased vessel site to complete accurate deployment and withdrawal.

Evaluation time: Intraoperatively (evaluation endpoint)

Evaluation site: target vessel

Evaluation method: The success rate of device operation is calculated by intraoperative evaluation of whether the delivery, deployment and withdrawal of the thrombectomy device are completed.

Formula: Device operation success = Number of devices delivered, deployed and withdrawn/Number of all investigational devices used in this group $\times 100\%$.

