2.2. Safety Endpoints

1. Incidence of symptomatic intracranial hemorrhage within 24 hours postoperatively: Symptomatic intracranial hemorrhage refers to intracranial hemorrhage (cerebral parenchymal hematoma, subarachnoid hemorrhage, subdural hematoma, ventricular hemorrhage) accompanied by neurological deterioration (NIHSS score increase ≥ 4 points compared to preoperative). Incidence of symptomatic intracranial hemorrhage within 24 hours = Number of subjects in this group with symptomatic intracranial hemorrhage confirmed by CT or MR within 24 hours / Number of subjects in this group undergoing intracranial thrombectomy with a thrombectomy stent $\times 100\%$. CT or MR findings were evaluated by the central reading center.
2. All-cause mortality within 90 days postoperatively: All-cause mortality rate = Number of deaths in this group / Total number of subjects in this group undergoing intracranial thrombectomy with a thrombectomy stent $\times 100\%$.
3. Incidence of SAEs, incidence of AEs.
4. Device defects rate.

3. Analysis Set

Full Analysis Set (FAS): A population defined according to the intention-to-treat principle, comprising all subjects who participated in randomization and received the study product. For patients in whom the primary efficacy endpoint was not observed, missing data will be carried forward using

the Worst Observation Carry Forward (WOCF) strategy.

Protocol-Compliant Set (PPS): Refers to the subgroup of the treated population that completed the trial, excluding those with major protocol deviations (e.g., subjects violating inclusion or exclusion criteria).

Safety Set (SS): Refers to the population of all subjects who used the study device and had at least one safety assessment.

Efficacy analyses will be conducted on the basis of the full analysis set and the per-protocol set. Additionally, all baseline demographic analyses will be performed on the full analysis set, while safety evaluations will be conducted on the safety set.

4. Missing Data Imputation

For patients in the FAS who did not have an observed primary efficacy endpoint, worst-case imputation was applied, defined as failure to achieve immediate reperfusion in the target vessel. No imputation was performed for secondary endpoints or efficacy data in the PPS. Missing safety data were not imputed.

5. Statistical Analysis Methods

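### The premature-termination visit always uses the Visit 5 content, so a subject who withdraws before Visit 3 or Visit 4 is done gives an unused early mRS and not the NIHSS still due

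*Protocol*

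**What the plan says.** Protocol section 6.2.1.3, item 6, applies to any withdrawal before follow-up ends: "an premature termination visit must be completed as soon as possible and the reason for termination will be recorded". It sets the content for every such visit, whenever it takes place: what is done in this "period is the same as Visit 5. All information will be analyzed and documented by the investigator".

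The visit being copied is the last one: "The subjects undergo outpatient/telephone follow-up 90 ± 14 d postoperatively". Its list is mRS, anticoagulant and antiplatelet drugs, and adverse events. NIHSS and CT/MR are not on it.

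The measurements that belong to the first days are at other visits:

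- **Visit 3**, "3) Visit 3: Observation period (V3: 24 ± 12 h postoperatively", has NIHSS and the only scheduled postoperative brain imaging: "iv. Cerebral CT or MR will be performed, and the following information will be recorded".
- **Visit 4**, at 7 ± 2 d or before an early discharge, has NIHSS but no imaging.

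Protocol section 6.1.6 evaluates the NIHSS responder endpoint before the operation and at "24 ± 12 h postoperatively and 7 ± 2 d postoperatively (before discharge in case of premature discharge"). Section 4 of the SAP says: "No imputation was performed for secondary endpoints or efficacy data in the PPS. Missing safety data were not imputed".

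Protocol section 6.1.5.3 also mentions the visit: "Subjects who withdraw early should be requested to complete an early withdrawal visit according to the visit schedule". It gives no separate content.

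**The concern.** The content of the termination visit is tied to the end of follow-up and not to the moment of withdrawal. Soon after the operation, that means the wrong scale is collected at a contact that takes place anyway. The disability score is taken when it cannot serve the 90-day endpoint, and the neurological score that is due at that moment is not taken.

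Such losses need not be neutral. Protocol section 6.1.5.3 names adverse events and failed corrective treatment among the reasons for withdrawal, and lets the investigator withdraw a subject on medical or safety grounds. Some of these subjects may be in poor condition, and some may still be in hospital where they could be examined.

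The endpoint formulas add to this. In Protocol sections 6.1.6 and 6.1.7 and SAP section 2, the NIHSS and haemorrhage rates divide by all treated subjects. Read literally, and with no imputation, an unassessed subject stays in the denominator and counts as a non-responder for NIHSS and as free of symptomatic haemorrhage. The SAP tables carry a missing count, so the analyst may drop such subjects instead. The SAP does not say which.

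**Working it through.** No figure in the plan depends on this rule, so the check sets visit windows against visit contents.

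**Windows** (Protocol section 6.2.1.3)

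- Visit 3: 24 ± 12 h = 12 to 36 h.
- Visit 4: 7 ± 2 d = day 5 to day 9, or earlier at discharge.
- Visit 5: 90 ± 14 d = day 76 to day 104.

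**What is still due and what is collected**

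| State at withdrawal | Still due for an endpoint | Collected at termination |
|---|---|---|
| By 36 h, Visit 3 not done | 24 h NIHSS, CT/MR, 7 d NIHSS, 90 d mRS | Early mRS, drugs, AEs |
| Visit 3 done or its window closed; up to day 9, Visit 4 not done | 7 d NIHSS, 90 d mRS | Early mRS, drugs, AEs |
| Visit 4 done, or after day 9 | 90 d mRS | mRS, drugs, AEs |

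NIHSS is the gap in the first two rows. CT/MR is a gap in the first row only. Its window is open for at most 36 h of the 9 days: 36 / (9 × 24) = 36/216 = 17% of the interval. In the third row no NIHSS or CT/MR is due, and the Visit 5 content fits.

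**Use of the early mRS.** An mRS taken by day 9 precedes the opening of the 90-day window by at least 76 − 9 = 67 days. Protocol section 6.1.6 and SAP section 2.1.2 define the endpoint at 90 days, and SAP Table 29 reports only the 90-day score. The worst-observation rule covers the primary endpoint only (Protocol section 8.4, SAP section 4). No rule assigns termination-visit data to any time point. So no planned analysis uses that mRS.

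**Reach.** Recanalization is read from the angiogram during the procedure (Protocol section 6.1.6), before this visit could occur. The sample size rests on that endpoint alone and reproduces: (1.96 + 0.842)² × 2 × 0.89 × 0.11 / 0.125² = 98.4, rounded up to 99; 99 / 0.90 = 110 per group. The pass/fail rule in Protocol section 8.2 names recanalization and unacceptable device-related safety issues, and no NIHSS result. The exposed endpoints are the NIHSS decrease at 24 h and 7 d and, for the earliest leavers, symptomatic haemorrhage within 24 h.

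**The case against.** **The plan already deals with early leaving.** Visit 4 is brought forward when a subject is discharged early, and section 6.1.5.3 ties the withdrawal visit to the visit schedule. The first point stands for discharge: such a subject has the later NIHSS, and the gap is smaller for it. It does not cover a subject who withdraws without, or ahead of, a discharge assessment, and Visit 3 has no such allowance. The section 6.1.5.3 sentence could be read as asking for whatever the schedule holds at that time. But the schedule's own entry for this visit is item 6, and that entry gives the Visit 5 content.

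**Haemorrhage is not lost altogether.** This stands. A reader might infer that haemorrhage status disappears for early leavers. The termination visit records adverse events, and Protocol section 13.3 exempts from its hospitalization criterion only haemorrhage judged not symptomatic, so a symptomatic one can still be reported as a serious event. What can be missed is the endpoint value, which needs the NIHSS change and centrally read imaging.

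**CT/MR.** A reader might also infer that everyone who leaves before day 9 misses CT/MR. The schedule does not support that: imaging is due once, and after 36 h none is outstanding.

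**Numbers.** It is tempting to take the 10% dropout allowance (0.10 × 220 = 22) as the pool of affected subjects. Protocol section 8.1 defines that rate as every condition that removes a subject from the primary analysis, including protocol deviations and loss to follow-up. It does not forecast withdrawals who attend a visit. Subjects who die or are lost to follow-up cannot attend, and some who withdraw will decline further assessment.

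**Conclusion.** The point holds in a narrow form. The rule in item 6 collects an unused mRS and omits the NIHSS for subjects who withdraw before Visit 3 or Visit 4 is completed, up to day 9. It omits CT/MR only for those who leave by 36 h without Visit 3.

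The conclusion about content rests on the text alone. Its size cannot be given: the documents state no number of early withdrawals and no split by time or reason, so probably few is as far as one can go. It touches a secondary endpoint and, at the margin, one safety endpoint. It does not touch the primary conclusion of the trial. This is a cheap improvement to a stated rule and not a flaw that threatens the result.

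**What to change.** **Protocol section 6.2.1.3, item 6.** Keep the Visit 5 content, which suits later withdrawals, and add: *plus any Visit 3 or Visit 4 assessment not yet done, if the subject agrees: NIHSS up to day 9, and the scheduled cerebral CT/MR up to 36 h postoperatively.*

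**SAP.** State that a termination NIHSS taken at 12 to 36 h is used for the 24 h time point, and that one taken after 36 h and up to day 9 is used as the 7-day or pre-discharge value. Without the second part, an NIHSS between 36 h and day 5 would fall in neither window and go unused, as the early mRS does now. A termination NIHSS before 12 h serves neither time point under this rule and should be listed only.

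**Cost.** One protocol sentence, one eCRF branch and one SAP sentence. The assessments are already scheduled for these subjects, so no new procedure is added. Two downsides remain: a bedside NIHSS at a contact that could otherwise be by telephone, and some 7-day values measured before day 5, which the pre-discharge allowance already permits.
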